### 1.2.3. Rate of Change Models

```
*****;
*** Rate of Change analyses ***;

* In this example, repeated measures are available at
* avisitn = 0 (baseline), 2 (Month 2), 4 (Month 4)
* 6 (Month 6), 8 (Month 8), 10 (Month 10) and 12 (Month 12)
*
* AVAL is the actual GA lesion measurement at the corresponding visit * for
the study eye from ADGA.
* SGALESAT is the GA lesion size (categorical) at baseline
* FCNVAT is the fellow eye CNV status at baseline
* TR01PG2N is the pooled treatment group (1 = PM, 2 = PEOM, 3 = Sham)
* T is equivalent to AVISITN
*
* The data is read in from ADGA
*****;
```

```
proc mixed data=ga method=reml covtest empirical;
```

```
class subjid TR01PG2N FCNVAT SGALESAT t;
model aval = SGALESAT TR01PG2N avisitn TR01PG2N * avisitn
          SGALESAT*avisitn FCNVAT/cl solution;
repeated t /type=un sub=subjid r ;

**Month 6;
estimate 'PM Month 0 to 6 slope' TR01PG2N*avisitn 6 0 0
          avisitn 6 SGALESAT*avisitn 3 3 /cl;
estimate 'PEOM Month 0 to 6 slope' TR01PG2N*avisitn 0 6 0
          avisitn 6 SGALESAT*avisitn 3 3 /cl;
estimate 'Sham Month 0 to 6 slope' TR01PG2N*avisitn 0 0 6
          avisitn 6 SGALESAT*avisitn 3 3 /cl;

estimate 'Month 0 to Month 6 Difference in slope PM - Sham'
          TR01PG2N*avisitn 6 0 -6 /cl;
estimate 'Month 0 to Month 6 Difference in slope PEOM - Sham'
          TR01PG2N*avisitn 0 6 -6 /cl;
estimate 'Month 0 to Month 6 Difference in slope PM - PEOM'
          TR01PG2N*avisitn 6 -6 0 /cl;

**Month 12;
estimate 'PM Month 6 to 12 slope' TR01PG2N*avisitn 6 0 0
          avisitn 6 SGALESAT*avisitn 3 3 /cl;
estimate 'PEOM Month 6 to 12 slope' TR01PG2N*avisitn 0 6 0
          avisitn 6 SGALESAT*avisitn 3 3 /cl;
estimate 'Sham Month 6 to 12 slope' TR01PG2N*avisitn 0 0 6
          avisitn 6 SGALESAT*avisitn 3 3 /cl;

estimate 'Month 6 to 12 Difference in slope PM - Sham'
          TR01PG2N*avisitn 6 0 -6 /cl;
estimate 'Month 6 to 12 Difference in slope PEOM - Sham'
          TR01PG2N*avisitn 0 6 -6 /cl;
estimate 'Month 6 to 12 Difference in slope PM - PEOM'
          TR01PG2N*avisitn 6 -6 0 /cl;

ods output diffs= diff2 LSMeans= LSMean2 CovParms = COV2
          estimates = estimates2;

**Month 0 to 12;
estimate 'PM Month 0 to 12 slope' TR01PG2N*avisitn 12 0 0
          avisitn 12 SGALESAT*avisitn 6 6 /cl;
estimate 'PEOM Month 0 to 12 slope' TR01PG2N*avisitn 0 12 0
          avisitn 12 SGALESAT*avisitn 6 6 /cl;
estimate 'Sham Month 0 to 12 slope' TR01PG2N*avisitn 0 0 12
          avisitn 12 SGALESAT*avisitn 6 6 /cl;

estimate 'Month 0 to Month 12 Difference in slope PM - Sham'
          TR01PG2N*avisitn 12 0 -12 /cl;
estimate 'Month 0 to Month 12 Difference in slope PEOM - Sham'
          TR01PG2N*avisitn 0 12 -12 /cl;
estimate 'Month 0 to Month 12 Difference in slope PM - PEOM'
          TR01PG2N*avisitn 12 -12 0 /cl;

run;
```

\* For the piecewise model, a knot at Month 6 is added to the dataset and included in the model to allow for different slopes for the two 6 month periods;

```
data ga2;
  set ga;

  k = 6;
  if avisitn <= k then avisitnspl1 = 0;
  if avisitn > k then avisitnspl1 = avisitn - k;
run;

proc mixed data=ga2 method=reml covtest empirical;
  class subjid TR01PG2N FCNVAT SGALESAT t;
  model aval = SGALESAT TR01PG2N avisitn avisitnspl1 TR01PG2N *
    avisitn TR01PG2N*avisitnspl1 SGALESAT*avisitn
    SGALESAT*avisitnspl1 FCNVAT/cl ;
  repeated t /type=un sub=subjid r ;

  **Month 6;
  estimate 'PM Month 0 to 6 slope' TR01PG2N*avisitn 6 0 0
    avisitn 6 SGALESAT*avisitn 3 3 /cl;
  estimate 'PEOM Month 0 to 6 slope' TR01PG2N*avisitn 0 6 0
    avisitn 6 SGALESAT*avisitn 3 3 /cl;
  estimate 'Sham Month 0 to 6 slope' TR01PG2N*avisitn 0 0 6
    avisitn 6 SGALESAT*avisitn 3 3 /cl;

  estimate 'Month 0 to Month 6 Difference in slope PM - Sham'
    TR01PG2N*avisitn 6 0 -6 /cl;
  estimate 'Month 0 to Month 6 Difference in slope PEOM - Sham'
    TR01PG2N*avisitn 0 6 -6 /cl;
  estimate 'Month 0 to Month 6 Difference in slope PM - PEOM'
    TR01PG2N*avisitn 6 -6 0 /cl;

  **Month 12;
  estimate 'PM Month 6 to 12 slope' TR01PG2N*avisitn 6 0 0
    avisitn 6 SGALESAT*avisitn 3 3 TR01PG2N*avisitnspl1 6 0 0
    avisitnspl1 6 SGALESAT*avisitnspl1 3 3 /cl;
  estimate 'PEOM Month 6 to 12 slope' TR01PG2N*avisitn 0 6 0
    avisitn 6 SGALESAT*avisitn 3 3 TR01PG2N*avisitnspl1 0 6 0
    avisitnspl1 6 SGALESAT*avisitnspl1 3 3 /cl;
  estimate 'Sham Month 6 to 12 slope' TR01PG2N*avisitn 0 0 6
    avisitn 6 SGALESAT*avisitn 3 3 TR01PG2N*avisitnspl1 0 0 6
    avisitnspl1 6 SGALESAT*avisitnspl1 3 3 /cl;

  estimate 'Month 6 to 12 Difference in slope PM - Sham'
    TR01PG2N*avisitn 6 0 -6 TR01PG2N*avisitnspl1 6 0 -6/cl;
  estimate 'Month 6 to 12 Difference in slope PEOM - Sham'
    TR01PG2N*avisitn 0 6 -6 TR01PG2N*avisitnspl1 0 6 -6/cl;
  estimate 'Month 6 to 12 Difference in slope PM - PEOM'
    TR01PG2N*avisitn 6 -6 0 TR01PG2N*avisitnspl1 6 -6 0/cl;

  ods output diffs= diff2 LSMeans= LSMean2 CovParms = COV2
    estimates = estimates2;
run;
```

#### 1.2.4. Sample Code for Maximum Reading Speed and Critical Print Size

Please see below regarding the uncorrected and corrected reading speed calculation, and Critical Print Size: Flag = 1 MNREAD , 2 = Radner .

```
if flag = 1 then do;
  if (time = 0 or notdone = 1) then urs = 0;
  /** "Not Done" indicates the print size was not attempted due to vision or
  that the sentence was attempted but could not be read **/
  else if time > 0 then urs = 600/time;
  if urs > 300 then urs = 300;
  /** Calculate Corrected Reading Speed **/
  if (time = 0 or numerr >= 10) or (notdone = 1) then crs = 0;
  else if numerr >= 0 and time > 0 then crs = 60*(10-numerr)/time;
  else if (numerr = 0 or time = 0) then crs = urs;
  if crs > 300 then crs = 300;
end;
if flag = 2 then do;
  if (time = 0 or notdone = 1) then urs = 0;
  else if time > 0 then urs = 840/time;
  if urs > 300 then urs = 300;
  if (time = 0 or numerr >= 14) or (notdone = 1) then crs = 0;
  else if numerr >= 0 and time > 0 then crs = 60*(14-numerr)/time;
  else if (numerr = 0 or time = 0) then crs = urs;
  if crs > 300 then crs = 300;
end;
Critical Print Size:
if flag = 1 and n(aval,dist) =2 and dist ne 40 then aval = aval +
round(log10(40/dist),.01); /** Apply correction for viewing distance ne 40
**/
if flag = 2 and n(aval,dist) =2 and dist not in (32 40) then aval = aval -
0.1 + round(log10(40/dist),.01);
```

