APPENDIX G: MINNESOTA LOW-VISION READING TEST (MNREAD) AND RADNER READING CARDS

The manual of procedures should be referenced for a detailed table of countries and languages to determine which test will be administered. Equipment and testing procedures will also be described in detail in the manual of procedures for both tests.

Minnesota Low-Vision Reading Test:

The Minnesota Low-Vision Reading Test acuity cards are continuous-text reading-acuity cards used for measuring the reading acuity and speed of normal and low-vision patients. These charts were developed at the Minnesota Laboratory for Low-Vision Research, University of Minnesota, Minnesota, USA.

The MNREAD Acuity Charts will be used to measure:

- Critical Print Size: the smallest print that the patient can read with maximum speed
- Maximum Reading Speed: the patient's reading speed when reading is not limited by print size

Radner Reading Cards:

The Radner Reading Cards consist of sentence optotypes, which are optimized reading test items, standardized by construction and statistical selection. These cards allow for accurate and comparable measurements of reading acuity and reading speed and measurement of critical print size.

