#### **6.4.3. Monocular critical print size**

Critical print size will be calculated as the smallest print size which support reading speed at 80% of the maximum reading speed, without adjustment for reading inaccuracy (Baskaran et al. 2019).

Monocular critical print size of the study eye will be summarized and analyzed in a similar fashion as the primary efficacy endpoint using MMRM described in Section 6.2.2. The model will include treatment (PM, PEOM, Sham), presence of CNV in the fellow eye (yes or no), and baseline GA lesion area ( $< 7.5 \text{ mm}^2$  or  $\geq 7.5 \text{ mm}^2$ ) as fixed effects; baseline monocular critical print size as well as the chart type (MNRead or Radner) as covariates, time (in months) as a factor; the time  $\times$  treatment interaction term as well as the baseline monocular critical print size  $\times$  time interaction term.

The observed values for the monocular critical print size will be summarized by treatment group and visit for both the study and the fellow eye. Summaries will present the descriptive statistics for baseline, absolute values and change from baseline data.

To assess the potential effect of different assessment tools, the analysis of monocular critical print size will be repeated by chart type.

All monocular critical print size data will be listed for the ITT set.

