## 6.5. Multiplicity Adjustment

No hypothesis testing of the (non-key) secondary endpoints will be performed. Control of Type I error for (non-key) secondary endpoints is not applicable.

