#### **13.5.3.3. Critical Print Size**

Critical print size will be calculated as the smallest print size which support reading speed at 80% of the maximum reading speed. If all wpm at all print sizes = 0 at a visit then that visit's critical print size will be missing. Print size needs to be adjusted for viewing distance as follows:

- Radner Charts:
  - For viewing distance of 32 cm
    - No correction is needed.

- For viewing distance of other than 32 cm:
  - $\text{Print size} = \text{Print size} - 0.1 + \text{correction}$ , where  $\text{correction} = \log_{10} [40 / (\text{viewing distance in cm})]$ , rounded to two decimal places

Note: the CRFs for the MNRead charts have print sizes pre-filled for a 40 cm viewing distance, while the Radner charts have print sizes pre-filled for a 32 cm viewing distance.

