### **13.7.6. Character Values of Clinical Laboratory Variables**

If the reported value of a clinical laboratory variable cannot be used in a statistical analysis (e.g., a character string is reported for a numerical variable), the appropriately determined coded value will be used in the statistical analysis, several examples are shown in [Table 8](#) for an illustration purpose. The actual values as reported in the database will be presented in data listings.

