## 1.2. Sample of SAS Code

\* The SAS codes in this section are shown as examples  
\* Some modifications (such as variables used in the model statement)  
\* may require further changes to reflect the methods specified in the  
\* SAP and analysis data structure  
\* e.g., change trtan to trtpn to reflect analysis w/ the ITT set;

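### Two small SAP clean-ups: the Radner sample code contradicts the SAP text at 40 cm (0.00 against -0.10), and Table 8 codes specific gravity '≤1.005' as 0.5025, below the Table 3 low limit

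*SAP*

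**What the plan says.** **Radner critical print size.** SAP section 13.5.3.3 applies no correction at 32 cm, the distance for which the Radner print sizes on the CRF are pre-filled. The other branch reads "For viewing distance of other than 32 cm", and there the print size is changed by -0.1 plus log10(40/distance), with the log term rounded to two decimals. The matching line in Appendix 1, section 1.2.4 begins "if flag = 2 and n(aval,dist) =2 and dist not in (32 40", so it leaves both 32 cm and 40 cm uncorrected. Section 1.2 introduces the programs with "The SAS codes in this section are shown as examples" and adds that they may need changing to match the SAP's methods.

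**Specific gravity.** SAP section 13.7.6 deals with laboratory results reported as strings and says that "the appropriately determined coded value will be used in the statistical analysis". Table 8 gives instances "for an illustration purpose". For urinalysis specific gravity it codes '≤1.005' as 0.5025 and '>1.030' as 1.030. Table 3 calls specific gravity potentially clinically significant (PCS) on the low side when it is under 0.9 × LLN, with the LLN supplied by the laboratory.

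**The concern.** On the first point, the text and the code cannot both be followed for a Radner test at 40 cm. If a programmer copies the code, critical print size is wrong for those tests. Section 6.4.3 would carry the error into its tables ("Summaries will present the descriptive statistics for baseline, absolute values and change from baseline data") and into the baseline covariate of the model. Maximum reading speed does not use this line.

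On the second point, halving a bound makes sense for a quantity that can approach zero. Specific gravity in Table 8 lies between about 1.005 and 1.030, so half of 1.005 is not a plausible value. Section 7.2 summarises specific gravity as observed values and changes and counts subjects with PCS values. The coding therefore creates low flags that no measurement supports and distorts the means.

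**Working it through.** **Radner correction**

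Inputs: reference distance 32 cm and the text formula (SAP 13.5.3.3); the code condition (SAP Appendix 1, 1.2.4).

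- Exact: log10(32/d)
- Text: 0 at d = 32, otherwise -0.1 + round(log10(40/d), 2)
- Code: as the text, but 0 at d = 32 and at d = 40

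| Distance (cm) | Exact | Text | Code | Code minus text |
|---|---|---|---|---|
| 20 | 0.204 | 0.20 | 0.20 | 0.00 |
| 25 | 0.107 | 0.10 | 0.10 | 0.00 |
| 32 | 0.000 | 0.00 | 0.00 | 0.00 |
| 40 | -0.097 | -0.10 | 0.00 | +0.10 |
| 50 | -0.194 | -0.20 | -0.20 | 0.00 |

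At 40 cm the text gives -0.1 + log10(40/40) = -0.1 + 0 = -0.10. Text and code also agree at 16, 30, 35 and 45 cm, so only 40 cm differs. The MNRead line also skips 40 cm, but harmlessly: its reference distance is 40 cm and log10(40/40) = 0. On the Radner line the same exemption drops the -0.1 term.

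Error in change from baseline = error at the visit minus error at baseline:

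- 40 to 40 cm: 0.10 - 0.10 = 0.00
- 32 to 40 cm: 0.10 - 0.00 = +0.10
- 40 to 32 cm: 0.00 - 0.10 = -0.10

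**Specific gravity**

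Inputs: coded values (SAP Table 8); low limit 0.9 × LLN (SAP Table 3). The LLN is not in the documents; I assume 1.000 to 1.020, on the scale of the Table 8 results.

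1. The plan's figure reproduces as 1.005/2 = 0.5025. Table 8 halves in the same way for bilirubin (<1.7 to 0.85, <2 to 1) and FSH (<0.2 to 0.1).
2. A value v is flagged low when v < 0.9 × LLN, that is, when LLN > v/0.9. For 0.5025: 0.5025/0.9 = 0.558. For 1.005: 1.005/0.9 = 1.117.
3. For LLN 1.000 to 1.020 the limit is 0.9 × 1.000 = 0.900 to 0.9 × 1.020 = 0.918. So 0.5025 is always flagged and 1.005 never is.
4. Each coded string is 1.005 - 0.5025 = 0.5025 too low compared with coding at the limit. If a share p of results arrives as this string, the mean falls by p × 0.5025: 0.005 at 1%, 0.025 at 5%, 0.050 at 10%. These shares are assumptions. For scale, the two reporting limits differ by 1.030 - 1.005 = 0.025.
5. A subject who goes from '>1.030' to '≤1.005' is shown a change of 0.5025 - 1.030 = -0.5275. With both coded at their limits it would be 1.005 - 1.030 = -0.025.

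**The case against.** **Radner.** The code is labelled as an example that may need adapting, so the text governs and harm arises only if the line is run unchanged. No document says that any Radner test was done at 40 cm; Protocol Appendix G leaves this to the manual ("Equipment and testing procedures will also be described in detail in the manual of procedures for both tests"), and the number affected could be zero. The section 6.4.3 model includes chart type, which would absorb part of an offset common to all Radner subjects, though not necessarily the part carried by the baseline-by-time term. The endpoint is not tested: "No hypothesis testing of the (non-key) secondary endpoints will be performed". All of this stands, and it makes the point close to clerical. It does not make the line correct. The line names 40 cm explicitly, and the SAP's revision history shows that version 2.0 already corrected sample code for reading speed.

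**Specific gravity.** Table 8 follows a pattern: upper-bound strings are coded at the limit and lower-bound strings are halved. So '≤1.005' is not an isolated slip. That is fair, and the real fault is applying halving to a scale that is not anchored at zero. Also, '≤1.005' is the only inclusive bound that is halved: pH '≥8.0' and protein '≥500' keep their limits. The rows are illustrations and the listings keep the reported value, so the odd code would be visible on review. But the row states a specific value, and section 13.7.6 sends coded values into the analysis.

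A last objection is that, on the assumed LLN range, the Table 3 low limit lies below 1.005, so after the edit the low flag would rarely or never fire. That follows from the figures above. It concerns how useful that limit is, and it does not justify flags produced by the coding.

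**Conclusion.** Both points hold, and both are minor. The Radner code is wrong at 40 cm by +0.10 log unit and right at every other distance checked. If a subject is always tested at 40 cm, the error stays in the baseline and absolute values and the baseline covariate; change from baseline is off by ±0.10 only when the distance moves to or from 40 cm. This rests on the code being run as printed, and the number of such tests is unknown.

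The Table 8 code gives a false low flag for every '≤1.005' string whenever the LLN exceeds 0.558, which covers any LLN on the scale of the table's own results. It also lowers the summaries by an amount that depends on an unknown share of such strings. Results reported as numbers are unaffected. Neither point touches the primary or key secondary analyses, alpha or power.

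**What to change.** 1. **SAP Appendix 1, section 1.2.4:** in the Radner line, replace the condition that excludes both 32 and 40 with `dist ne 32`. The correction at 40 cm is then -0.10, as in section 13.5.3.3.
2. **SAP Table 8:** code specific gravity '≤1.005' as 1.005, at its limit, as is already done for '>1.030'. Table 3 needs no change for this.

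The cost is two one-line SAP edits, with no new data and no change to any tested endpoint.
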